The index date (start date of medical record abstraction for the first patient) for the study will be selected for each country and correspond to the date when a site becomes aware of the study objectives. After all approvals from national EC and regulatory authorities have been granted, all medical record data will be retrospectively reviewed until the index date; this approach will ensure the data collected are fully reflective of real world administration of MabThera and not influenced by study awareness. The retrospective review of medical records will occur within a 12-month "look-back" period prior the selected index date (i.e., the eligibility period). The observation period for consenting patients corresponds to the interval between the first and last infusion dates of MabThera, if treatment is discontinued before the index date. If the patient is still on MabThera at the index date, then the observation period is the interval between the first infusion date and index date. Furthermore, if a patient stops and re-starts MabThera during the observation period, all repeated treatment intervals will be captured.

Patient Alert Card survey

The PAC survey will be conducted after the index data and concomitantly with the medical record abstraction process. The PAC survey will be completed once by each patient after informed consent has been provided.

Duration of the study

The planned duration of the study (i.e., both medical record and survey data collection) is approximately 16 months after the recruitment of the first patient. This period takes into account 10 months of data collection and a 6 month period between last patient recruited and final study report.

will closely monitor inclusion rates. If projected recruitment rates indicate that patient targets may not be achieved in the planned recruitment period, consideration will be given to extending the recruitment period, initiating additional sites within the 5 existing countries, and/or expanding the study into additional EU countries.

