8.3 VARIABLES

Medical Record Data

The site will abstract information from the medical record for each of the DUS consenting patients and will enter the abstracted information in an electronic case report form (eCRF):

- Study ID (identification), age, sex
- Condition for which MabThera has been prescribed (via checklist):

- RA
- Ankylosing spondylitis
- Psoriatic arthritis
- Undifferentiated spondyloarthritis
- Juvenile idiopathic arthritis
- SLE
- Systemic vasculitis
- Inflammatory myopathies
- Behçet disease
- Sjögren syndrome
- Nephrotic syndrome
- Reason for MabThera prescription:
 - Failure of previous treatment
 - Adverse events (AEs) under previous treatment
 - Compassionate use
- Date of first diagnosis of the condition
- For patients with RA, severity of RA as measured with the DAS28 (28-joint Disease Activity Score). To calculate the DAS28, the following items will have to be abstracted from the medical record:
 - C-reactive protein level
 - Erythrocyte sedimentation rate
 - Number of tender joints
 - Number of swollen joints
 - Global assessment of patient's general health on the visual analogue scale (VAS) (0–100)
 - Presence of extra-articular involvement
- MabThera dosage for the most recent infusion and number of MabThera infusions in the past 2 years
- Other current and previous anti-inflammatory medication including biological agents other than MabThera
 - Methotrexate (key variable for on- or off-label classification of MabThera use)

- Glomerulonephritis
- Multiple sclerosis/neuromyelitis optica
- Pemphigus vulgaris
- Polydermatomyositis
- Mixed connective tissue disease
- Wegener's GPA/ MPA
- Eosinophilic GPA
- Other (specify)

- Immunosuppressives: prednisolone, glucocorticoid bolus therapy, methylprednisolone, methotrexate, cyclophosphamide, azathioprine, mycophenolate mofetil, intravenous immunoglobulin, plasmapheresis, other immunosuppressives (specify)
- Non-steroidal anti-inflammatory drugs (NSAIDs), including cyclooxigenase (COX)-2 inhibitors
- Biological agents:
 - TNF-alpha inhibitors (key variable for on- or off-label classification of MabThera use): etanercept, infliximab, adalimumab, golimumab, certolizumab pegol, ocrelizumab
 - Interleukin inhibitors: tocilizumab, anakinra
 - Abatacept
 - Janus kinase (JAK) inhibitor: tofacitinib
 - Other biological agents (specify)

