8.6 DATA ANALYSIS

Analysis of MabThera off-label use and evaluation of PAC knowledge and utilisation will be descriptive in nature and will entail the tabular display of summary statistics and the frequency distribution of item responses.

A detailed analysis plan describing methods of analysis and presentation, as well as table shells, will be developed prior to starting analysis of data. In addition to describing the analysis of off-label use, for the questionnaire data, the analysis plan will describe any planned comparisons of participants and non-participants. The analysis plan will also describe the following:

- Analysis of subgroups
- · Methods for handling missing data
- Level of statistical precision

All analyses will be performed using SAS 9.2 (or higher) statistical software (SAS Institute Inc., Cary, North Carolina, USA). Programs, logs, and output will be reviewed for accuracy according to relevant standard operating procedures.

The analysis of off-label use will be descriptive and will present MabThera utilisation by indication (RA, SLE/LN, other). Results will be evaluated by site characteristics, including country and geographic region within country, to ascertain any patterns of prescribing by specific indication. The main analysis will be to estimate (with 95% CIs)

^a With an average cluster size of 8 patients, correlation coefficients of 0.15 and 0.30 correspond with design effects of 2.05 and 3.1, respectively.

^b The percentage in this column does not need to represent only the percentage of correct responses; it can represent any percentage, for example percentage of abstractions that were identified as off-label use or percentage of abstractions that had systemic lupus erythematosus (SLE).

the proportion of off-label use among users of MabThera during the entire study period in the 5 European countries of interest. The proportion of each of the most common off-label use indications will be described among the entire off-label use group. In addition, an estimate of off-label usage will be determined amongst prevalent (i.e., repeat infusions) and incident (i.e., patients attending for their first MabThera infusion) patients to the extent that incident use can be accurately determined. Characteristics of patients meeting the definitions for both strict and broad on-label use will also be evaluated. The dosage of MabThera used by infusion will also be estimated in the on- and off-label groups.

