Make sure you have a list of all your medicines when you see a health care professional.

Please talk to your doctor or nurse if you have any questions about the information in this card.

1.	Date of abstraction:	/	(dd/	mm/yyyy)
2.	Date of patient's most recent v	visit to infusion ce (dd/mm/yyyy)	entre:	
3.	Patient's age:			
	 □ 18-25 years □ 26-35 years □ 36-45 years □ 46-55 years □ 56-65 years □ 66-75 years □ 76-85 years □ > 85 years 			
4.	Patient's gender: ☐ Male ☐ Female			
5.	Date of patient's first MabTher (dd/mm/yyyy)	ra infusion:	/	/
6.	Date of patient's most recent I	MabThera infusio (dd/mm/yyyy)	n:	

7.		imary condit Select one a		tient wa	as prescribed MabThe	era:
		Rheumatoi	id arthritis*		Nephrotic syndrome	
		Ankylosing	spondylitis		Glomerulonephritis	
		Psoriatic a	rthritis		Multiple sclerosis/ne	uromyelitis optica
		Undifferent spondyloai			Pemphigus vulgaris	
		Juvenile id arthritis			Polydermatomyositis	;
		Systemic lu			Mixed connective tiss	sue disease
		Systemic v			Wegener's granulom polyangiitis	atosis/microscopic
		Inflammato myopathies			Eosinophilic granulo	matosis with
		Behçet dis	ease		polyangiitis	
		Sjögren sy	ndrome		Other (specify)	
	* C	omplete the S	upplemental Form f	or Patien	nts Receiving MabThera fo	or Rheumatoid Arthritis.
8.	Da	ate of first di	agnosis for prima	ary con	dition:	
		/	/	(dd/m	m/yyyy)	
9.		Failure of p Adverse ev Compassion	ase specify:	nt ious tre		
10.	То	tal number	of MabThera infu	usions i	n the past 2 years:	infusions
11	Ma	abThera dos	sage for most red	cent infi	ısion:	ma

12.	Medications patient has taken within the past 12 months. (Select all that apply.)
	Immunosuppressives
	□ Azathioprine
	☐ Cyclophosphamide
	□ Intravenous immunoglobulin
	☐ Methotrexate
	☐ Methylprednisolone (oral or in bolus)
	☐ Prednisolone (oral or in bolus)
	☐ Glucocorticoid (in bolus)
	☐ Mofetil mycophenolate
	□ Plasmapheresis
	☐ Other immunosuppressive, please specify:
	Non-steroidal anti-inflammatory drugs (NSAIDS)
	□ NSAIDS including COX-2 inhibitors
	Biological agents
	Tumour necrosis factor-alpha inhibitors
	□ Adalimumab
	☐ Certolizumab pegol
	□ Etanercept
	☐ Golimumab
	□ Infliximab
	□ Ocrelizumab
	Interleukin inhibitors
	□ Anakinra
	□ Tocilizumab
	Other biological agents
	□ Abatacept
	☐ Janus kinase inhibitor: Tofacitinib
	☐ Other, please specify:

Medical Record Abstraction Form—Draft

Supplemental Form for Patients Receiving MabThera for Rheumatoid Arthritis

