RA1.	☐ Yes☐ No	•	A1, contin	nue with	RA1	a. If n	o, go to RA2. otrexate use:
		/	/		(dd/n	nm/yy	уу)
RA2.	ever take		ur necrosi	s factor	-alph	a inhi	treatment cycle, did the patient bitors (adalimumab, iximab)?
in time		r to the dat					ts for tests performed closest ion in the patient's current
RA3.	C-reactive	ve protein (CRP) leve	el at first	t Mab	Thera	infusion in the current
	treatmer	nt cycle:		mmol	/L		
	RA3a.	Date of CI	RP test:	/		/	(dd/mm/yyyy)
RA4.	Erythroc	yte sedime	ntation rat	te (ESR) at fi	rst Ma	abThera infusion in the current
	treatmer	nt cycle:	mm/h	r			
	RA4a.	Date of ES	SR:	/	/		(dd/mm/yyyy)

RA5.	Tender j	oint count (0 – 28) at first Mab	Thera infu	ısion in t	he current	treatment
	cycle:	joints				
	RA5a. (dd/mm/	Date of tender joint count:	/	/		
RA6.	Swollen	joint count (0 - 28) at first Mat	Thera inf	usion in	the curren	t treatment
	cycle:	joints				
	RA6a. (dd/mm/	,	/	/		
RA7.		e of extra-articular involvemen reatment cycle:	t at first M	labThera	a infusion i	n the
RA8.		ssessment of patient's genera) at first MabThera infusion in				scale (VAS)
		mm				
	RA8a. (dd/mm/	Date of global health assessr	ment:	/	/	

Medical Record Abstraction Form—Draft

For questions RA9 through RA14a, please provide results for tests performed on or nearest to the date of the patient's most recent MabThera infusion (Q6).

RA9. C-reactive protein (CRP) level at most recent MabThera infusion:

mmol/L Date of CRP test: RA9a. (dd/mm/yyyy) RA10. Erythrocyte sedimentation rate (ESR) at most recent MabThera infusion: mm/hr RA10a. Date of ESR: (dd/mm/yyyy) RA11. Tender joint count (0 - 28) at most recent MabThera infusion: joints RA11a. Date of tender joint count: (dd/mm/yyyy) RA12. Swollen joint count (0 - 28) at most recent MabThera infusion: joints RA12a. Date of swollen joint count: (dd/mm/yyyy) RA13. Presence of extra-articular involvement at most recent MabThera infusion: ☐ Yes □ No

	sessment of patient's general health or at most recent MabThera infusion:	n visu	al ar	nalogu	e scale	(VAS)
	mm					
RA14a. (dd/mm/y	Date of global health assessment:	/		/		

3. Patient Questionnaire - Draft

MabThera Risk Minimisation Programme Evaluation

Patient Questionnaire—Draft

Thank you for agreeing to participate in this study.

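### The protocol ends record review at the index date, but section 8.3 and the draft abstraction form set no such limit and have no fields for the promised treatment intervals

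*Protocol*

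**What the plan says.** Protocol section 8.1.1 states that "all medical record data will be retrospectively reviewed until the index date". The stated purpose is to keep the data free of any effect of the site knowing about the study. For a patient still on treatment, the observation period also ends at the index date. The same section says that the index date is the start of abstraction for the first patient and that it will "correspond to the date when a site becomes aware of the study objectives". For patients who stop and restart, it says that "all repeated treatment intervals will be captured".

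Section 8.3 lists the exposure variables as "MabThera dosage for the most recent infusion and number of MabThera infusions in the past 2 years". The draft form in Appendix 1 follows this pattern:

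- Q2 and Q6: dates of the most recent visit and infusion.
- Q10 and Q11: infusion count over the past 2 years, and dose at the latest infusion.
- Q12: "Medications patient has taken within the past 12 months".
- RA9–RA14a: RA tests on or nearest the latest infusion, for example "RA9. C-reactive protein (CRP) level at most recent MabThera infusion", with mmol/L as the unit.

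Section 8.6 adds: "The dosage of MabThera used by infusion will also be estimated in the on- and off-label groups".

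**The concern.** The index date protects the utilisation component from reactive prescribing and recording. That protection works only if the data items respect the date, and none of the items above mentions it. A coordinator who completes the form as printed will give the latest infusion, dose, tests and drugs at the time of abstraction, which may be months after the site learned the objectives.

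The affected items are dose, co-medication and latest RA severity. Section 8.3 marks methotrexate as key to classifying use as on- or off-label, and section 8.6 plans to describe patients meeting strict and broad on-label definitions. These descriptions could mix practice before and after awareness, with no field on the form to separate the two.

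The second gap concerns capture. A promise to record every treatment interval needs fields that hold intervals, and no later analysis plan can recover data that were not collected.

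**Working it through.** The protocol gives no figure on this point to reproduce. The check compares the sections and works out how much of each window can fall after the index date.

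**Inputs**

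- Cut-off: the index date (section 8.1.1).
- Entry: the patient attends for an infusion during the study period (section 8.2).
- Collection: up to 10 months, starting with the first abstraction (section 8.1.1 and Figure 1).
- Windows: 12 months for medication (form Q12) and 24 months for the infusion count (section 8.3, form Q10).
- Assumption: each window runs back from the day of abstraction (form Q1), since the form gives no other anchor.

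**Windows.** For abstraction m months after the index date (m = 0 to 10), the post-index share of calendar time is m/12 and m/24.

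| m | 12-month window | 24-month window |
|---|---|---|
| 0 | 0/12 = 0% | 0/24 = 0% |
| 5 | 5/12 = 42% | 5/24 = 21% |
| 10 | 10/12 = 83% | 10/24 = 42% |

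These are shares of calendar time. They show how far post-index data can enter, not how many recorded drugs or infusions are post-index. With every item limited to the index date, both columns become 0% for every m.

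**Single-date items (Q2, Q6, Q11, RA9–RA14a).** If the record is abstracted after the infusion visit at which the patient entered, and that visit follows the index date, the latest infusion and its dose are post-index. If it is abstracted shortly before the visit, which section 8.2 allows for eligibility checks, the latest infusion may be pre-index. The form accepts both and does not distinguish them.

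**Intervals.** Per patient the form holds two infusion dates (first, Q5; latest, Q6), one 2-year count (Q10) and one dose (Q11). Take two patients with the same first date, latest date and count, one treated continuously and one who stopped and restarted. Their entries would be identical, so the intervals cannot be derived. The list in section 8.3 is no fuller.

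**Index date.** Section 8.1.1 equates it with both the first abstraction and the site's awareness of the objectives. Section 8.2 has centres contacted to confirm eligibility and interest, and asked during recruitment about alert-card distribution and counselling. Figure 1 puts site selection and contracting in a start-up phase before data collection. The two dates will not normally coincide.

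**The case against.** Section 8.1.1 forbids post-index review, so the form fails to enforce a rule rather than overriding it. The form is also a draft that may be adjusted after its pilot. Both points are fair. But section 8.3 in the protocol body uses the same unanchored wording, and a site works from the form.

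Several stronger readings are tempting but not supported:

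- *The whole form is tied to the latest infusion.* It is not. First infusion (Q5), diagnosis date (Q8), any earlier TNF-inhibitor use (RA2) and RA status at the first infusion of the current cycle (RA3–RA8) are separate items. RA1 and RA1a also appear to record methotrexate use with a date.
- *The main result is biased.* Section 8.3 defines off-label use by disease, and the main analysis in section 8.6 rests on the primary condition (Q7), which these windows hardly touch.
- *Planned analyses have no data.* Section 8.6 plans no interval analysis, so what fails is a capture promise. Dosage by infusion can be read as dose per infusion by group, which Q11 supplies.
- *Every patient contributes 10 months of post-index data.* The amount depends on when each record is abstracted and whether that patient's infusion, test or drug falls after the index date.
- *DAS28 will be understated by a known amount.* The documents give no DAS28 formula and no other CRP unit, and ESR is collected as well. Any size would need an outside formula and sites that truly convert to molar values. Copying the laboratory's figure would only mislabel it.

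**Conclusion.** The point holds as an inconsistency between the design in section 8.1.1 and the data items in section 8.3 and Appendix 1. As drafted, between 0% and 83% of the medication window and between 0% and 42% of the infusion-count window can lie after the index date, for abstraction 0 to 10 months after it. This assumes that the windows count back from abstraction. Dose, co-medication and latest RA severity are affected; the disease-based off-label proportion is not materially affected. Separately, the promise to capture all repeated treatment intervals cannot be kept with the fields provided, and the index date has two meanings that need reconciling.

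The CRP unit is secondary. The form prints mmol/L at RA3 and RA9. I assume that the DAS28 formula to be used takes mg/L, which the documents do not state, so this is an item to check and not an error of known size. These corrections should be made before the form is piloted.

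**What to change.** 1. Record the site's index date on the form. In section 8.3 and in Q2, Q6, Q10–Q12 and RA9–RA14a, replace the open wording with *last visit or infusion on or before the index date* and *12 (or 24) months before the index date*.
2. Flag patients with no infusion before the index date and report them separately. Section 8.2 admits patients at a study-period visit and section 8.6 wants first-infusion patients, so sections 8.1.1, 8.2 and 8.6 must be reconciled.
3. Add start and stop dates for each treatment interval, or delete that promise from section 8.1.1. State in section 8.6 that dosage by infusion means the dose at the last pre-index infusion, unless more doses are collected.
4. Define the index date once. Do not backdate it to feasibility contact. That work in 30 centres fed into protocol version 1.0 of 27 July 2012, so for any of those centres a 12-month look-back would fall before the March 2013 GPA/MPA approval and the present on-label definition would not fit.
5. Name the DAS28 formula and check the CRP unit at RA3 and RA9 against it.

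The cost is a few more fields per patient on a draft form, and some records without a pre-index infusion.

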6.2 MABTHERA

Rituximab (MabThera®) is a genetically engineered chimeric murine/human monoclonal antibody, which binds specifically to CD20, a B-lymphocyte differentiation antigen on pre-B and mature B-lymphocytes. In June 2006, the United States (US) Food and Drug Administration had approved MabThera for RA (Food and Drug Administration, 2006). In June 2006, the European Medicines Agency (EMA) approved the use of rituximab for the same indication. The RA indication was updated by Variation EMEA/H/C/165/II/65 (EMA, 2010). The current European Union (EU) approved label authorises MabThera in combination with methotrexate for the treatment of adult patients with severe, active RA who have had an inadequate response or intolerance to other disease-modifying anti-rheumatic drugs including one or more tumour necrosis factor (TNF) inhibitor therapies.

In March 2013, the EMA approved a new non-oncology-related indication, allowing the use of MabThera in combination with glucocorticoids for the induction of remission in adult patients with severe, active GPA (Wegener's) and MPA (EMA, 2013a). Rituximab is also approved for several oncology conditions, but these indications are not the focus of this study.

This protocol addresses the 2 EU follow-up measures (FUMs) following approval of Variation EMEA/H/C/165/II/65 for MabThera use in RA.

1. FUM no. 68 (Clinical): Drug Utilisation Study to Assess Off-Label Use

There is concern regarding off-label use of MabThera, in particular that rheumatologists and other physicians may prescribe MabThera for systemic lupus erythematosus (SLE) and lupus nephritis (LN). The EMA Committee for Medicinal Products for Human Use (CHMP) FUM (Clinical) No. 68 from Procedure No. EMEA/H/C/165/II/65 states, 'Given the extensive off-label potential of MabThera, the MAH [Marketing Authorisation Holder] should submit a European drug utilisation study protocol to the CHMP'.

2. FUM No, 71.1 (Pharmacovigilance): Evaluation of Receipt, Use, and Impact of the Patient Alert Card (PAC) on Infections, Including Progressive Multi-focal Leukoencephalopathy (PML)

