A "data not available" response will be available where appropriate for those record abstraction items for which data may be missing from patient records. This type of response will help reduce missing data and will document the overall gaps in record keeping.

A brief pilot test of the translated version of the abstraction form will be conducted in each country, and the abstraction form in one or more countries may be adjusted based on the results of this pilot.

A draft version of the medical record abstraction form is included with this document (Appendix 1).

Off-Label Use Definition

The definition of off-label use of MabThera will be based on the use for a non-oncology disease or medical condition other than RA and GPA/MPA covered by MabThera SPC.

In absence of labelled indications, potential off-label use could include, but is not limited to, the following conditions:

- Ankylosing spondylitis
- Psoriatic arthritis
- Undifferentiated spondyloarthritis
- Juvenile idiopathic arthritis
- SLE
- Systemic vasculitis

- Eosinophilic GPA
- Inflammatory myopathies
- Behçet disease
- Sjögren syndrome
- Nephrotic syndrome
- Glomerulonephritis
- Multiple sclerosis/neuromyelitis optica
- · Pemphigus vulgaris
- Polydermatomyositis
- · Mixed connective tissue disease

Patient Survey data

The patient questionnaire has been developed following standard survey methodological principles and will be cognitively tested with patients in each of the target countries. Modifications will be made to the questionnaire based on the results of testing, and some variations to the questionnaire are anticipated based on country-specific requirements.

The questionnaire will include an introductory section with questions to confirm eligibility. The majority of the questionnaire items will be closed ended, ensuring that the resulting data are easy to analyse and interpret. Closed-ended questions are generally more efficient than open-ended questions (or open-ended text fields) and more conducive to summarisation and statistical analyses.

The questionnaire will collect the following information (please refer to Appendix 1 for the draft questionnaire):

- Demographics (e.g., age, sex, ethnicity)
- Patient previous history of PML or other serious infectious diseases
- Whether the patient has received a previous treatment with MabThera, if so, number of prior infusions during the last 12 months
- Patient understanding or awareness of the following:

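### Section 8.3 and draft form Q12 file ocrelizumab, an anti-CD20 antibody, under TNF-alpha inhibitors, a variable named as key for on/off-label classification

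*Protocol*

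**What the plan says.** Protocol Section 8.3 sets out the medication data to be abstracted. One entry reads "TNF-alpha inhibitors (key variable for on- or off-label classification of MabThera use): etanercept, infliximab, adalimumab, golimumab, certolizumab pegol, ocrelizumab". The draft Medical Record Abstraction Form in Appendix 1 makes the same grouping. Its Q12, headed "Medications patient has taken within the past 12 months", gives ocrelizumab a tick-box under the TNF-alpha inhibitor sub-heading, and it has a separate group for other biological agents.

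The supplemental form for RA patients has its own item, RA2, on whether the patient ever took a TNF-alpha inhibitor. In the copy at hand its drug list survives only as "bitors (adalimumab, iximab", after which the bracket closes.

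Three further statements bear on what the variable is for:

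- Section 6.2 gives the RA label as covering patients "who have had an inadequate response or intolerance to other disease-modifying anti-rheumatic drugs including one or more tumour necrosis factor (TNF) inhibitor therapies".
- Section 8.3 says that the off-label definition will be "based on the use for a non-oncology disease or medical condition other than RA and GPA/MPA covered by MabThera SPC".
- Section 8.6 adds: "Characteristics of patients meeting the definitions for both strict and broad on-label use will also be evaluated".

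**The concern.** Ocrelizumab binds CD20, the target that Section 6.2 gives for MabThera itself. It does not belong in a list of TNF-alpha inhibitors. The grouping occurs in both Section 8.3 and Q12, so it is not an isolated slip of the pen and would pass into the eCRF as written.

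The variable has a purpose. The RA label refers to TNF-inhibitor therapy, Section 8.3 calls the class key to classification, and Section 8.6 plans to describe strict and broad on-label groups. If TNF history is taken from the list as printed, an RA patient with ocrelizumab and no true TNF inhibitor counts as TNF-exposed. In a strict class that requires TNF history, that is an error towards on-label. Q12 sits on the general form for all indications, so a table of TNF-inhibitor use by indication would carry the same error.

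The forms also seem to disagree. If RA2 omits ocrelizumab, the same patient is TNF-exposed on Q12 and unexposed on RA2.

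**Working it through.** The plan states no figure for this point, so the check is mainly a comparison of texts.

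**1. The three lists.**

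| Place | TNF-alpha inhibitors listed | Ocrelizumab |
|---|---|---|
| Section 8.3 | etanercept, infliximab, adalimumab, golimumab, certolizumab pegol, ocrelizumab | included |
| Form Q12 (past 12 months) | adalimumab, certolizumab pegol, etanercept, golimumab, infliximab, ocrelizumab | included |
| Form RA2 (ever taken) | adalimumab, [lost], a name ending in -iximab, bracket closes | apparently absent |

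Q12 is in alphabetical order. A list that opens at adalimumab and closes at infliximab fits the same order with ocrelizumab left off. This is an inference from damaged text. The error in Section 8.3 and Q12 does not depend on it, because both of those lists are intact.

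**2. Which outputs can be affected.**

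- *Main off-label proportion (Section 8.6).* The definition in Section 8.3 uses indication only. Every RA patient is on-label whatever drugs came before, so the change is 0 points for any number of ocrelizumab patients.
- *Strict on-label group (Section 8.6).* It can be affected if its rule uses TNF history taken from the Section 8.3 or Q12 list. The protocol does not state the rule.
- *Tables of TNF-inhibitor use by indication.* They are affected if they are built from the Q12 sub-heading.

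**3. Size per patient.** Let *k* be the number of patients with ocrelizumab as the only drug ticked in the TNF group, and *n* the number of records (1,000 to 1,500 in Section 8.5). The share with TNF history is overstated by *k/n*. The documents give no value for *k*; the values below are assumed, only to show the scale.

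| k (assumed) | n = 1,000 | n = 1,500 |
|---|---|---|
| 0 | 0 | 0 |
| 1 | 1/1,000 = 0.10 points | 1/1,500 = 0.07 points |
| 5 | 0.50 points | 0.33 points |
| 15 | 1.5 points | 1.0 point |
| 30 | 3.0 points | 2.0 points |

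Among RA patients alone the denominator is smaller than *n*, and its size is not given, so the overstatement there would be larger than *k/n* for the same *k*.

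**4. Scale.** Section 8.5 gives a 95% interval of 72.8% to 77.2% for 75% of 1,500 records. The formula p ± 1.96 × √(p(1 − p)/n) gives 0.75 ± 1.96 × √(0.75 × 0.25/1,500) = 0.75 ± 0.022, which reproduces it. One misfiled patient (0.07 points) is small against a half-width of 2.2 points.

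**The case against.** The strongest reply is that little depends on the error. The main estimate rests on indication and cannot move. RA2, the RA-specific item that asks about use at any time, is a more natural source for TNF history than Q12 with its 12-month window, and RA2 may already be right. The form is a draft that Section 8.3 expects to pilot and perhaps adjust. The SAP, which is not shown, may define the strict class without using Q12.

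Most of this stands and limits the point to a narrow one. It does not remove the point, because the protocol text itself fixes the content of a class that it calls key. An analysis plan that follows the variable as written would inherit the error.

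A reader might infer more, and the documents do not support it:

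- *That an ocrelizumab-only patient is recorded as meeting the label's TNF condition.* Section 6.2 speaks of inadequate response or intolerance, not use, and no stated rule turns a tick in Q12 into a condition met.
- *That earlier anti-CD20 treatment is concealed.* Ocrelizumab keeps its own tick-box in Q12, so it can be regrouped at analysis without loss.
- *That the trial-participation exclusion in Section 8.2, which applies only to the survey, makes such patients likely in the record component.* That exclusion concerns trials evaluating MabThera and says little about ocrelizumab exposure.
- *That Section 8.3 and RA2 are proven to conflict.* The middle of the RA2 list is lost, so the conflict remains apparent only.

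**Conclusion.** The grouping is wrong in Section 8.3 and in Q12, and it appears to conflict with RA2. An RA patient whose only such drug was ocrelizumab would be recorded under the TNF-inhibitor heading. This could misclassify that patient in the strict on-label group and in tables of TNF-inhibitor use. The effect on the main off-label proportion is 0 points.

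The number of patients affected is unknown and may be zero. The documents offer no basis for a percentage, so none is claimed.

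The conclusion rests on two assumptions. First, ocrelizumab is an anti-CD20 antibody; this is general pharmacology that the protocol does not state. Second, for any effect on the strict class, its rule would have to draw TNF history from the list as printed. This is a small correction, worth making because it is in a variable named as key and is easiest to put right before the eCRF is built.

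**What to change.** 1. In Section 8.3, form Q12 and the eCRF specification, move ocrelizumab from the TNF-alpha inhibitors to the other biological agents, keeping its own tick-box.
2. Read RA2 in the original form, and make the TNF-inhibitor list identical in Section 8.3, Q12 and RA2.
3. Derive the TNF-history variable for the strict on-label class from the corrected list, and state which form item supplies it.

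The cost is one line moved in each place and a check of RA2. No data item is added and the study size is unchanged. If records have already been abstracted, the separate tick-box allows the drug to be regrouped in the analysis data set without going back to the sites.
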